# 8.4.3. Confirmed Cases of DENV (Part B)

For **Part B**, confirmed cases of DENV will be recorded on an AE Form throughout the full duration of the study. The incidence of DENV will be summarized as the number and percentage of subjects tabulated by treatment arm overall and stratified by baseline ZIKV Status. 95% CIs will be included along with p-values from Chi-Square test (Table 107, Appendix 1).

# 8.5. Pregnancies

Female subjects of childbearing potential will receive pregnancy prevention counseling throughout the study. Women will be asked to notify the site immediately if they suspect or learn they are pregnant during this study. In case of pregnancy, subjects will be removed from the product administration schedule but may have limited clinic contacts and blood draws at the discretion of the site PI and IND Sponsor. The pregnancy outcomes are captured by the Pregnancy eCRF.

A table summarizing the total pregnancies, number of live births, miscarriages, elective abortions, ectopic pregnancies, still births, congenital anomalies, and neonatal deaths by treatment will be presented (Table 108 for Part A, Table 109 for Part B, Appendix 1). In addition, a listing of pregnancies and outcomes will be presented (Listing 40 for Part A and Listing 41 for Part B, Appendix 3).

# 8.6. Clinical Laboratory Evaluations

Planned safety laboratory parameters include: alanine aminotransferase (ALT), white blood cells (WBC), red blood cells (RBC), hemoglobin, hematocrit, mean corpuscular volume (MCV), platelets, neutrophils, lymphocytes, monocytes, eosinophils, and basophils. Laboratory safety evaluations are scheduled at baseline and weeks 4, 6, 8, 10, 12, 16 for **Part A**, and at baseline and weeks 4, 8, 16, 20, for **Part B**.

Only results for planned parameters and scheduled visits will be included in summaries. Safety laboratory evaluations are graded as follows: mild (grade 1), moderate (grade 2), severe (grade 3), or partially life threatening (grade 4) following the grading criteria in Protocol Appendix IV. Any abnormal laboratory results are reported as unsolicited AEs, and thus summarized as described in Section 8.3.2.

Safety laboratory results will be summarized for each parameter by study visit and study group. Continuous summary statistics for each parameter along with standard deviation for the mean will be presented in Table 117 through Table 119 for Part A and Table 120 - Table 121 for Part B (Appendix 1). Box plots for each parameter will be included in Figure 55 through Figure 66 for Part A and Figure 67 through Figure 78 for Part B (Appendix 2). Each boxplot will show the 1st quartile, the median, and the 3rd quartile, with values smaller than the 1st quartile or larger than the 3rd quartiles plotted as outliers. If appropriate, horizontal lines representing boundaries for abnormal values will be plotted.

Continuous summary statistics for the change from baseline for each parameter along with standard deviation for the mean will be presented in Table 117 through Table 119 for Part A and Table 120 - Table 121 for Part B (Appendix 1). Each Safety laboratory parameter will be summarized using shift tables to compare baseline and follow-up values (Table 122 through Table 147 for Part A and Table 148 through Table 166 for Part B, Appendix 1). Shift tables will be analyzed using Generalized Estimating Equations (GEE) to account for the longitudinal nature of these data, as follows:

- 1) For laboratory parameters with two categories: Normal and abnormal (Binary response)
  - a. For each parameter the shift table displays the number of subjects categorized as normal and abnormal at baseline cross tabulated with normal and abnormal results at the post-product administration visit.
  - b. A GEE for the binary responses above is fitted and used for parameter estimation
    - Observation  $(y_{ii}, X_{ii})$  for each subject i = 1, ..., n and repeated measurement
    - time point j = 1, ..., J• dependent variable  $y_{ij} = \begin{cases} 1 & abnormal \\ 0 & normal \end{cases}$ , independent variable  $X_{ij} = \begin{cases} 1 & abnormal \\ 0 & normal \end{cases}$ (groupii, timeii, groupii \* timeii);
    - probability of abnormal is  $p_{ii} = Pr(y_{ii} = 1)$ ;
    - model:  $g(p_{ii}) = X'_{ii}\beta$  using the logit link;
    - GEE:  $\sum_{i=1}^{n} \left( \frac{\partial P_i}{\partial \beta} \right) V_i^{-1}(\alpha) (Y_i P_i) = 0$  where  $V_i(\alpha)$  is the working covariance matrix:
    - Implementation: PROC GENMOD (SAS) using SUBJECT option in the REPEATED statement to identify the cluster variable

- Output: point estimates and 95% CI for the individual levels of the GROUP, TIME and GROUP\*TIME variables, and Type-3 SAS output for the parameter significance;
- Other analysis and outputs: Odds ratio with associated 95% CI of observing abnormality (from the fitted logistic model). Implemented with LSMEANS statement in PROC GENMOD.

# 2) For laboratory parameters with three categories: Low, Normal and High (Ordinal response)

- a. For each parameter the shift table displays the number of subjects who are categorized as low, normal, or high at baseline cross tabulated with low, normal or high results at the post-vaccination visit.
- b. A GEE model for the ordinal responses above is fitted and used for parameter estimation
  - Observation  $(Y_{ij}, X_{ij})$  for each subject i = 1, ..., n at time point j = 1, ..., J.  $Y_{ij} = (y_{ij1}, y_{ij2})$  is the ordinal response variable with 3 ordered categories;
  - Cumulative probability pijk = Pr(yijk = 1: in lower k category) = Pr(Yij ≤ k), k = 1,2;
  - Proportional Odds model  $\begin{cases} g(p_{ij1}) = \mu_1 + X'_{ij}\beta \\ g(p_{ij2}) = \mu_2 + X'_{ij}\beta \end{cases}$  using the logit link;
  - $X'_{ij}\beta = -\beta_1 t_{ij} + \beta_2 group_{ij} + \beta_3 t_{ij} * group_{ij}$
  - GEE:  $\sum_{i=1}^{n} \left(\frac{\partial P_i}{\partial \beta}\right) V_i^{-1}(\alpha) (Y_i P_i) = 0$  where  $P_i = E(Y_i) V_i(\alpha)$  is the working covariance matrix;
  - Output: estimates of two intercepts from the two fitted logistic models; point estimates and 95% CI for the individual levels of the GROUP, TIME and GROUP\*TIME variables, and Type-3 SAS output for the parameter significance (chi-Square test);

The study is not powered to detect differences by study group, therefore the absence of statistically significant differences should not be interpreted as no such differences exist.

Individual clinical laboratory results will be presented for subjects with abnormal results of Grade 2 or higher for at least one parameter from at least one visit, including planned parameters collected at scheduled visits as well as any other parameters collected, and any results for unscheduled visits in Table 167 for **Part A** and Table 168 for **Part B**, **Appendix 1**.

# 8.7. Vital Signs and Physical Evaluations

Vital signs measurements include oral temperature, pulse, systolic and diastolic blood pressure, and respiratory rate. The assessment of vital signs is planned at baseline and weeks 4, 6, 8, 18, 12, and 16 for **Part A**, and at baseline and weeks 4, 8, 16, 44, 72, and 96 for **Part B**. Vitals are collected

pre- and post-study product administration. Vitals are also captured on the Visit Documentation eCRF at visits 6, 13, 20 and 26. A targeted physical exam is conducted at the same time points as the vital signs assessment and recorded in the subject's chart but not reported in the study database.

Vital signs will be summarized for each parameter by study visit, assessment (pre- or post-administration, if applicable), severity grading and study group (Table 174 through Table 176 for **Part A** and Table 177 - Table 178 for **Part B**, **Appendix 1**). Box plots for each parameter will be included in Figure 103 through Figure 106 for **Part A** and Figure 107 through Figure 110 for **Part B** (**Appendix 2**).

#### 9. IMMUNOGENICITY EVALUATION

The principal immunogenicity endpoints are measured at Day 0 (Visit 02) and 4 weeks after the third administration (Visit 05) by NAb. We assume NAb results will follow a log-normal distribution.

The following summaries will be presented by study group and study visit separately for Part A and Part B for all subjects in each of the ITT, PP and mITT analysis populations. Summaries are presented over all subjects and stratified by baseline ZIKV serostatus.

- The number and percentage of subjects with positive NAb response, defined as a titer≥30, along with their exact 95% CIs and p-values from a Chi-squared test comparing study groups. (Table 19 through Table 24, Appendix 1)
- GMTs and their CIs, p-values from a t-test comparing log-NAb titers between study groups. (Table 25 through Table 30, Appendix 1)
- Geometric mean fold rise (GMFR) in NAb from baseline with the corresponding confidence interval and (1) p-value from a paired t-test comparing the log-NAb titers between baseline and post-administration within each treatment arm, and (2) p-value from t-test comparing log-transformed fold increases in NAb between study groups. Non-parametric tests will be considered if the normality assumption is not realized. (Table 25 through Table 30, Appendix 1)
- Boxplots of NAb titers. (Figure 15 through Figure 26, Appendix 2)
- Reverse cumulative distribution curves of NAb titers. (Figure 3 through Figure 14, Appendix 2)

Exploratory analysis of NAb for other visits will be presented in a similar fashion as data are available.

A listing of individual NAb titer levels, whether positive and the corresponding planned and actual collection dates are presented in Listing 16 - Listing 17, **Appendix 3.** For any immunogenicity reports released prior to database lock and study unblinding, a coded subject identifier will be included in listings to prevent unblinding any subject's study product assignment.

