#### Part B:

- To evaluate the magnitude and the frequency of ZIKV-specific antibody response as measured by neutralization assay at 4 weeks after the last product administration.
- To compare incidence rates of subclinical cases of ZIKV infection in vaccine and placebo recipients.

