# 6.2.2. Immunogenicity

The principal immunogenicity endpoints are 4 weeks after the last product administration compared to Day 0 as measured by neutralization assay. Exploratory immunogenicity endpoints are measured by neutralization assay, ELISA, and other research tests as described in Section 1.7.

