# 6.4.3. Analysis of Immune Responses

Immunogenicity will be analyzed for a variety of cohorts defined above, and specified in the SAP (Statistical Analysis Plan). At minimum these may include ITT, PP, and mITT cohorts. Assay results will be examined to determine if their distributions should be analyzed as normal, lognormal, nominal or categorical. It may also be appropriate to dichotomize the data into "responders" and "non-responders". Immunogenicity data will be analyzed at each time point where such data is collected. Longitudinal methods will be used to estimate the nature and extent of immune response decay over time. Immunogenicity will be assessed by group. To account for preexisting immunogenicity due to prior ZIKV exposure, immunogenicity will also be assessed according to baseline serostatus as a secondary analysis.

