#### 6.4. Covariates and Subgroups

All immunogenicity analyses will be conducted overall and stratified by baseline ZIKV seroprevalance for all Part A and Part B subjects. Additional summaries may be tabulated by clinical site, but the study is not powered for any additional subgroup analyses.

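### Positive neutralizing-antibody response ignores the Day 0 titer, so the all-subjects and baseline-positive rates describe seropositivity at the visit, not response

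*Combined protocol and SAP*

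**What the plan says.** Protocol section 3.2 gives both parts the same secondary immunogenicity objective: "To evaluate the magnitude and the frequency of ZIKV-specific antibody response as measured by neutralization assay at 4 weeks after the last product administration". Frequency of response is therefore a stated target alongside magnitude. Protocol section 6.2.2 adds the reference point: "The principal immunogenicity endpoints are 4 weeks after the last product administration compared to Day 0 as measured by neutralization assay". Section 6.4.3 leaves open whether and how to split subjects into responders and non-responders, and deals with earlier infection as follows: "To account for preexisting immunogenicity due to prior ZIKV exposure, immunogenicity will also be assessed according to baseline serostatus as a secondary analysis".

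SAP section 9 settles the split. It tabulates "The number and percentage of subjects with positive NAb response, defined as a titer" of at least 30; the rule and its test read: "positive NAb response, defined as a titer≥30, along with their exact 95% CIs and p-values from a Chi-squared test comparing study groups". It sets no Day 0 condition and no separate rule for subjects already at or above the cut-off. The Table 21 shell (SAP Appendix 1) counts responders on the pre-administration row as well as at Visit 05.

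The same section contains two safeguards. On stratification: "Summaries are presented over all subjects and stratified by baseline ZIKV serostatus"; SAP section 6.4 repeats this for both parts. On change from baseline: "Geometric mean fold rise (GMFR) in NAb from baseline with the corresponding confidence interval", with a paired test within arm and a t-test between groups.

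Seropositive subjects can enrol. Protocol section 4.1.2 excludes only a self-reported confirmed history of infection, and the Part B planning in section 6.3.2.3 covers 0% to 30% seropositive at baseline. The SAP takes baseline serostatus from Visit 01 serum (section 3.2.1), the protocol from Visit 02 (section 6.4). Neither names an assay or a cut-off.

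**The concern.** An absolute cut-off applied at the visit cannot separate antibody raised by the vaccine from antibody that was already there. A previously infected placebo recipient with a titer of 30 or more is a responder, and so is a previously infected vaccinee whose titer has not moved. The all-subjects rate then mixes vaccine response with the infection history of the site. The baseline-positive rate may be high in every arm before any product is given.

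At stake are the reported response frequency and its between-group chi-square test. In Part B the size of the effect would be understated. In Part A, which has no placebo arm, the rates would be inflated and the regimens harder to tell apart. The Part B regimen has already been chosen (protocol section 1.5), so in Part A the consequence is for the reported comparison.

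**Working it through.** **The plan's own figures.** Protocol section 6.3.2.2 applies Table 7 to the Part B response rate. With a two-sided chi-square test (pooled variance, 5% error, no continuity correction), 1200 per group and a 10% placebo rate, the detectable difference is 3.69 points at 80% power and 4.32 at 90%, as printed. The 24 cells of Table 7 that were checked, across all four sample sizes, agree within 0.01 point. The Table 3 intervals, used for the Part A response rate, also reproduce with Clopper-Pearson limits (0/30: upper bound 0.116; 5/30: 0.056 to 0.347). No stated figure is wrong; the point concerns the definition.

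**Effect of the definition.** Let s be the baseline seropositive share, and r_v and r_p the rates of reaching 30 among seronegatives on vaccine and placebo. Assume every seropositive subject has a titer of 30 or more at baseline and at Visit 05. Then:

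- all-subjects rate in an arm = s + (1 − s) × r
- all-subjects difference = (1 − s) × (r_v − r_p)

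The added s cancels between randomized arms, and what remains is shrinkage by (1 − s).

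**Part B, 1200 per group.** The documents give no response rates. Assume r_p = 2% and r_v = 70%:

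| s | placebo | vaccine | difference |
|---|---|---|---|
| 0% | 2.0% | 70.0% | 68.0 points |
| 10% | 0.10 + 0.90 × 0.02 = 11.8% | 0.10 + 0.90 × 0.70 = 73.0% | 61.2 points |
| 30% | 0.30 + 0.70 × 0.02 = 31.4% | 0.30 + 0.70 × 0.70 = 79.0% | 47.6 points |

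With r_v at 50% or 90%, the difference at s = 30% is 33.6 points (from 48) or 61.6 points (from 88). Power is near 100% in every case. The difference among seronegatives does not depend on s.

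**Part A, 30 per group.** Assume two regimens with true rates of 50% and 80% among seronegatives. Power = Φ{[|p1 − p2| − 1.96 × √(2p̄(1 − p̄)/n)] / √[(p1(1 − p1) + p2(1 − p2))/n]}, where p̄ is the mean of p1 and p2.

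| s | all-subjects rates | power, all subjects (n = 30) | power, seronegatives only |
|---|---|---|---|
| 0% | 50% v 80% | 69% | 69% (n = 30) |
| 10% | 55% v 82% | 62% | 64% (n = 27) |
| 30% | 65% v 86% | 47% | 53% (n = 21) |

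At s = 30%, the fall from 69% to 53% comes from having fewer subjects below the cut-off at entry. The further fall from 53% to 47% comes from counting the others as responders. The 0% to 30% range is Part B planning and is carried to Part A as an assumption.

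**Does the baseline-negative panel equal seroconversion?** Only if baseline-negative means a Day 0 titer below 30. With no assay or cut-off stated, and different visits named in the two documents, that link is not made. Some subjects classed as negative could already be at or above 30, and some classed as positive could be below it.

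**The case against.** The strongest reply is that the useful analysis is already planned. In the baseline-negative panel a titer of 30 or more is, in effect, seroconversion. The pre-administration row shows how many were positive before vaccine. Fold rise with paired and between-group tests meets the Day 0 comparison of protocol section 6.2.2 and measures the vaccine effect in baseline positives. Part B is randomized against placebo, and the test is not short of power. Most of this stands, and it keeps the point small.

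A reader might therefore go too far in three ways:

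- *The response rate does not measure response at all.* The documents do not support this, because the baseline-negative panel comes close to doing so.
- *In the baseline-positive panel both arms sit near 100% whatever the vaccine does.* That can happen, but it is not established, since serostatus-positive is not defined as a titer of 30 or more.
- *The rule favours vaccine.* It does not. The dilution acts equally in both arms.

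The safeguards still leave gaps. Fold rise answers magnitude, whereas the objective also names frequency. Serostatus analysis is secondary under protocol section 6.4.3. The titles of the per-protocol response tables (SAP Tables 23, 26, 29 and 32) omit serostatus, although section 9 promises stratification.

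**Conclusion.** The point holds for the all-subjects and baseline-positive rates: as defined, they are seropositivity at the visit and do not make the Day 0 comparison in the protocol endpoint. No planned summary gives a frequency of response for baseline positives, and the baseline-negative panel is not tied to a Day 0 titer below 30.

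The size depends on s, and on the assumption that seropositive subjects have titers of 30 or more. The all-subjects difference loses nothing at s = 0, 10% of its size at s = 10% and 30% at s = 30%, the upper end of the planning range rather than an expected value. In Part B this is a matter of interpretation. In Part A the power cost can be material under the assumed rates. The endpoint is secondary and the primary efficacy test is unaffected, so the priority is low.

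**What to change.** In SAP section 9, define response from each subject's own Day 0 titer:

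- Day 0 below 30: response is a Visit 05 titer of 30 or more.
- Day 0 of 30 or more: response is a pre-specified fold rise from Day 0.

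Four-fold is one possible threshold, but the documents give no basis for it. Protocol section 1.7 describes three-fold serial dilutions with the EC50 from non-linear regression, and no assay variability is reported. The sponsor should justify the threshold from that variability.

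Use the definition for the overall and stratified comparisons. Make the rate among subjects below 30 at Day 0 the headline, so that seroconversion and boosting are not pooled in the main figure. Keep a titer of 30 or more over all subjects as a descriptive rate, relabelled as seropositivity. State the assay, cut-off and visit for baseline serostatus, reconciling Visit 01 with Visit 02, and add serostatus to the per-protocol response tables.

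The cost is one definition and one derived variable. Baseline and Visit 05 titers are already planned, and SAP section 3.2.1 already defines the baseline value and fold rise. The overall response percentage will look lower. The change should be made before the immunogenicity data are unblinded.

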## 1.7. Assessment of Immunogenicity

In this study, specimens to evaluate immunogenicity will be collected at baseline and at specified time points. The primary immunogenicity time point is 4 weeks after receipt of the last product administration. ZIKV-specific humoral immune responses will be assessed at clinical visits through 32 weeks after receipt of the first product administration in **Part A** and 96 weeks after receipt of the first product administration in **Part B**. ZIKV-specific cellular immune responses at baseline and select timepoints after product administration may also be assessed in Part A subjects and at designated sites in Part B.

NAbs are a well-established correlate of protection against flavivirus infection. A pseudoinfectious ZIKV RVP NAb assay will be performed at baseline and 4 weeks after the last product administration for a secondary endpoint as previously described for WNV [38, 39] and possibly on stored samples from other study time points as an exploratory endpoint. Use of the RVP approach to detect and enumerate NAbs offers several advantages as compared to the traditional PRNT including: increased precision, speed, and ability to perform assays under biosafety level-2 conditions in large scale (allowing analysis in replicate using a large number of dilutions). The normalization criteria used to validate assay results are derived directly from the "percentage law" (law of mass action) and confer a significant improvement in assay-to-assay reproducibility and accuracy. Extensive analysis of the neutralization potency of several well characterized monoclonal antibodies [57, 58] reveal agreement with published values obtained using the PRNT and BHK-21 cells [59].

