In general, descriptive statistics by vaccine group will be tabulated for all variables of interest, stratified by baseline ZIKV testing results. This will include point estimates (mean, geometric mean, median or proportions) and their respective 95% CI or percentile spread. Formal comparisons will use standard methods, contingency tables for categorical variables, t-tests or non-parametric analogs for comparing means or geometric means, logistic regression and analysis of covariance for model discrete and continuous variables respectively.

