- For efficacy analyses subjects who do not have at least one post-administration efficacy assessment (at least one visit or PCR (or other Zika) result) following product administration 3.
- *For immunogenicity analyses* subjects who do not have NAb results 4 weeks post product administration 3 (Visit 05) or at baseline.
- For immunogenicity analyses subjects with serum sample for 4 weeks post product administration 3 (Visit 05) collected outside the protocol specified window (Day 77 to Day 91).

Subjects may be censored from the Per-Protocol Analysis for any of the following:

- Receipt of any non-study inactivated vaccination within 2 weeks of any study product administration.
- Receipt of any live attenuated vaccination within 4 of any study product administration.

- Receipt of any other investigational research agent at any time during the trial.
- Receipt of any concomitant medication that may interfere with immune response, including but not limited to:
  - Any systemic immunosuppressive or cytotoxic medical blood products within 16 weeks prior to randomization.
  - Immunoglobulin within 8 weeks prior to randomization.
  - Current anti-TB prophylaxis or therapy.
- Confirmed or suspected immunosuppressive or immunodeficient condition, including HIV infection.

All exclusions from analysis populations and censoring events will be reviewed by the Protocol Statistician, Protocol Chairs, and Lead Medical Officer and others on the Protocol Safety Review Team.

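### SAP section 9 compares NAb between groups with one t-test that ignores the Day 0 titer and one that fixes its slope at 1; a single ANCOVA on Day 0 titer would be modestly more precise in the pooled comparison

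*Combined protocol and SAP*

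**What the plan says.** SAP section 9 names the time points: "The principal immunogenicity endpoints are measured at Day 0 (Visit 02) and 4 weeks after the third administration (Visit 05) by NAb". Protocol section 1.7 schedules the same two measurements: "A pseudoinfectious ZIKV RVP NAb assay will be performed at baseline and 4 weeks after the last product administration for a secondary endpoint". The SAP works on the log scale: "We assume NAb results will follow a log-normal distribution".

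Two between-group tests on magnitude follow. The first is "GMTs and their CIs, p-values from a t-test comparing log-NAb titers between study groups". The second, given with the geometric mean fold rise, is a "p-value from t-test comparing log-transformed fold increases in NAb between study groups". Non-parametric tests are the fallback if normality fails. No model has the Day 0 titer as a covariate.

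Baseline therefore enters in two ways only: through the fold-rise, and through presentation by a binary status: "Summaries are presented over all subjects and stratified by baseline ZIKV serostatus". Missing values are foreseen, because the per-protocol immunogenicity analysis excludes "subjects who do not have NAb results 4 weeks post product administration 3 (Visit 05) or at baseline".

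Protocol section 6.4 lists t-tests or non-parametric analogs for means and geometric means. The same sentence goes on to "logistic regression and analysis of covariance for model discrete and continuous variables respectively". ANCOVA is thus available under the protocol but is not tied to NAb.

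**The concern.** The two tests are the two extremes of how a baseline value can be used. A t-test on Visit 05 titer sets the baseline slope to 0, and a t-test on log fold-rise sets it to 1. ANCOVA estimates the slope from the data.

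The trial enrols in endemic or potentially endemic areas, and protocol section 6.3.2.3 plans for 0% to 30% seropositive at entry. Day 0 titers may therefore vary a good deal and carry through to Visit 05. The titer test leaves that variation in its error term. The fold-rise test can add noise when the true slope is well below 1.

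At stake is precision on a secondary endpoint, chiefly in Part A, where each arm has 30 subjects and the SAP table shells compare groups pairwise. A smaller point is that the two tests can give different p-values, and SAP section 9 does not say which one leads.

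**Working it through.** **Inputs.** Part A has 30 per group, a two-sided 5% level and effects in SD units on the log scale (protocol section 6.3.1.2, Table 5). Part B has 1200 per group and SD 1 (protocol section 6.3.2.2, Table 8). Rho, the correlation between log Day 0 and log Visit 05 titer, is not in the documents and is varied as an assumption. The pre-dose and post-dose SDs are assumed equal.

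**Step 1: reproduce the plan.** Noncentral-t power for a two-sample t-test at n=30 and effects of 0.5, 0.6, 0.7, 0.8 and 0.9 SD gives 47.8, 62.8, 76.0, 86.1 and 92.9%. Table 5 states 48, 63, 76, 86 and 93%. For n=1200 and SD 1 the detectable difference at 80% power is 0.114, against 0.11 in Table 8. Both reproduce, and neither uses baseline.

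**Step 2: variance factors.** The variance of the group difference is 2v/n in SD² units, with

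- titer t-test: v = 1
- fold-rise t-test: v = 2(1 − rho)
- ANCOVA: v = 1 − rho²

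Then 1 − (1 − rho²) = rho², and 2(1 − rho) − (1 − rho²) = (1 − rho)². Neither can be negative, so in large samples ANCOVA is never less precise than either test. It ties with the titer test at rho 0 and with fold-rise at rho 1. The two t-tests tie at rho 0.5.

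**Step 3: power at n=30 per arm, 0.5 SD.** The noncentrality is d / √(2v/n), with 58 degrees of freedom for the t-tests. For ANCOVA, 57 degrees of freedom are used and v is multiplied by 1 + 1/(2n − 4) = 1.018 to allow for chance baseline imbalance. Example at rho 0.5: v = 0.75 × 1.018 = 0.763, so the noncentrality is 0.5 / √(2 × 0.763/30) = 2.22, against 0.5 / √(2/30) = 1.94 for the titer test.

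| rho | titer | fold-rise | ANCOVA | gain over better t-test |
|---|---|---|---|---|
| 0 | 47.8% | 27.0% | 47.1% | −0.7 |
| 0.1 | 47.8% | 29.5% | 47.5% | −0.3 |
| 0.3 | 47.8% | 36.3% | 50.7% | 2.9 |
| 0.5 | 47.8% | 47.8% | 58.7% | 10.9 |
| 0.7 | 47.8% | 69.1% | 75.2% | 6.1 |

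Without the 1.018 factor, ANCOVA power at rho 0.3, 0.5 and 0.7 is 51.4, 59.4 and 76.0%, so the gains are 3.6, 11.6 and 6.9 points. At 0.8 SD and rho 0.5 the figures are 86.1, 86.1 and 93.6%. At 0.8 SD and rho 0.7 they are 86.1, 97.6 and 98.8%.

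**Step 4: detectable difference at 80% power**, using the large-sample factors, for titer / fold-rise / ANCOVA:

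- n=30: 0.736 / 0.736 / 0.637 SD at rho 0.5; 0.736 / 0.570 / 0.525 SD at rho 0.7
- n=1200: 0.114 / 0.114 / 0.099 at rho 0.5; 0.114 / 0.089 / 0.082 at rho 0.7

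**Step 5: titers at the assay floor.** Log titers in a mixed population are not bivariate normal, so a simulation was run. Assumed: every seronegative has the same floor value at Day 0, one arm stays at baseline apart from noise in seropositives, and the other is boosted mainly in seronegatives. Standard errors at n=30 for titer / fold-rise / ANCOVA:

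- 30% seropositive: 0.429 / 0.219 / 0.203
- 10% seropositive: 0.310 / 0.206 / 0.202
- 0% seropositive: 0.182 for all three, since baseline does not vary

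At n=1200 and 30% seropositive they are 0.069 / 0.034 / 0.031. The ordering holds, but the gain over fold-rise is small. The scenario resembles vaccine against placebo more than one Part A regimen against another, so it checks direction and does not size the Part A gain.

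**The case against.** The strongest objection concerns size. A reader might set 76% against 48% at rho 0.7, or 51% against 36% at rho 0.3, and infer gains of 28 and 15 points. The SAP runs both t-tests, and each of those contrasts picks the weaker one at that rho. Against the better one the gain is about 3 to 12 points. That stands. So does the absence of rho from the documents: at rho of 0.1 or less, ANCOVA at n=30 loses 0.2 to 0.8 points.

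A reader might also infer that ANCOVA matters most in the small serostatus strata. The material does not support this. Seronegatives are likely to be the majority and probably sit at or near the assay floor, where there is almost nothing to adjust for. The gain is mainly pooled, and the SAP already reports by serostatus.

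Nor does the SAP depart from the protocol. Protocol section 6.4 names ANCOVA generically and, in the same sentence, t-tests for geometric means.

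Finally, no success criterion rests on these p-values. The secondary objectives are to evaluate the magnitude and frequency of response. Comparing injections in 2 or 4 limbs is an exploratory Part A objective, and SAP section 2.1 leaves exploratory endpoint analyses out. The Part B regimen was already chosen (protocol précis and section 1.5), so extra Part A power cannot affect that choice. This limits the importance of the point but does not make the unadjusted tests preferable.

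Loss of subjects without a Day 0 titer is a real but small cost. They already drop out of the fold-rise test, and SAP section 6.5 plans no imputation for immunogenicity.

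**Conclusion.** The point holds as an efficiency improvement to a secondary analysis. The planned t-tests are valid. For the all-subjects comparison with equal allocation, ANCOVA on log Day 0 titer is at least as precise as either, apart from under 1 point of power when rho is near 0. At 30 per arm and 0.5 SD the gain over the better planned test is about 3 points at rho 0.3, 11 to 12 at rho 0.5 and 6 to 7 at rho 0.7. These figures rest on an assumed rho and equal pre-dose and post-dose SDs.

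The benefit lies mainly in final reporting of the pooled Part A comparisons. It is negligible among seronegatives at the floor. In Part B, where 0.11 is already detectable at SD 1, it amounts to a narrower interval. A single adjusted comparison would also settle which result leads.

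**What to change.** In SAP section 9, make the between-group comparison of magnitude one ANCOVA of log Visit 05 titer on group and log Day 0 titer, adding baseline serostatus in the pooled analysis. Report the adjusted GMT ratio with 95% CI. Keep GMT, geometric mean fold rise and the by-serostatus summaries as descriptive, and keep the non-parametric fallback.

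Two rules need a sentence each. Subjects without a Day 0 titer are left out of the model, as they already are for fold-rise, and their number is reported. Titers below the assay limit take the same assigned value as in the GMTs. Serostatus and Day 0 titer will be strongly related, so their own coefficients should not be interpreted; the group ratio is the target.

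The table shells need a matching edit. The Table 33 shell appears to show dashes where section 9 calls for between-group p-values on fold-rise, so text and shell have to be reconciled in any case. The cost is SAP wording, a shell change and a short model statement; no new data are needed.
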